10.0 Measurement of Effect

Because this study is a feasibility study and patients enrolled in this study will have distinct disease sites and heterogeneous treatment plans, measurement of treatment response will be at the discretion of treating radiation oncologist.

11.0 STATISTICAL CONSIDERATIONS

11.1 Definition of Primary Endpoint

Feasibility: Feasibility will be defined as successful completion of online adaptive proton radiotherapy workflow through treatment delivery in at least 70% of planned adaptive fractions..

Success will be defined as PARTy plan creation and delivery of the fraction using the study workflow in one on-table attempt. Unsuccessful planning and workflow delivery will be defined as multiple attempts of the PARTy workflow for one treatment fraction without treatment delivery such that the study workflow is abandoned.

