1.4 Preliminary Studies

The following is a proposed workflow for online adaptive proton therapy. This workflow draws upon our institutional expertise in MR-guided and CT-guided online adaptive radiotherapy.

[figure not shown]

Fig. 1 Proposed online adaptive proton radiotherapy workflow

[figure not shown]
The process initiates with the daily acquisition of CT images using our in-room CT-on-rails system. These images are imported into RayStation, where adjustments to contours and volumes are made by our dosimetry team with an overseeing physician. A physician is present at the machine to review, approve these contours and adjust contours as needed. Subsequently, the plan undergoes reoptimization and passes through an in-house physics quality assurance (QA) algorithm. The physician then conducts a final review of the adapted plan and grants approval. A formal treatment plan is generated and loaded onto the

treatment machine. To ensure no significant setup changes have occurred during the adaptation process, an additional CT image is acquired.

Investigation into the technical and logistical feasibility of the proposed workflow has been performed through an in-silico analysis. This study utilized patients who underwent proton therapy for rectal cancer recurrence as part of the IMPARC clinical trial (NCT04827732). Specifically, eight patients with rectal or other pelvic malignancies, previously treated on a proton dose escalation trial over five fractions, routinely received daily CT-on-rails imaging prior to each fraction.

We determined that the average time required to complete the online adaptive process ranged from 33 to 45 minutes.¹³ In typical proton planning, robust optimization and evaluation are employed, incorporating a 5mm setup uncertainty and a 3% proton range uncertainty for non-adaptive proton plans. However, for adaptive plans, we have the flexibility to eliminate setup uncertainty and optimize and evaluate with only a 3% proton range uncertainty, thereby reducing the dose to organs at risk (OAR) (figure 2).

5mm, 3%

0mm, 3%

[figure not shown]

Fig 2. 5mm setup uncertainty and a 3% proton range uncertainty for non-adaptive plans vs 0mm setup uncertainty and 3% proton range uncertainty for adaptive plans

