5.0 TREATMENT PLAN

The treatment will consist of stereotactic body radiation therapy, administered as 5 fractions. All patients will undergo standard initial consultation, pre-treatment simulation, and planning in accordance with institutional standards. When patients present for each treatment, the initial pre-plan will be generated and assessed for safety and coverage of the treatment area. In addition to this, a new adapted plan will be generated. Both plans will then be compared, and the plan deemed to be most appropriate will be carried out. This process will occur for each treatment.

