5.1.6 Adaptive Treatment Planning

When patients present for each proton treatment session, the initial treatment pre-plan will be generated based on the anatomy of the day. In addition to this, a new adapted treatment plan will be generated and re-optimization will be performed for dose adaptation to allow for acceptable sparing of normal structures (i.e., not violating the predetermined hard constraints based on safety constraints that are

already approved of for routine, clinical use). Dose adaptation can also be done in cases where on the volumetric imaging attained, there is noted to be violation of previously met hard constraints.

The supervising physician will review the adapted plan and prior non-adapted scheduled plan. Comparison will be made with initial pre-plan assessing for meeting OAR constraints and/or improvement of target coverage. The decision to proceed with the adaptive radiation is under the treating physician's clinical discretion where they feel tumor coverage may be impacted by interfraction motion of patient's anatomy and adaptive treatment may improve coverage based on pre-specified criteria (typically improvement in radiation dose coverage of the tumor or reduction of excess dose to a nearby organ which would increase toxicity). Subsequently, decision will be made if treatment will proceed with adapted plan or with initial pre-plan.

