11.4 Statistical Analysis Plan

The primary objective is to demonstrate that online proton adaptive radiotherapy is feasible by confirming that adaptive treatment can be delivered in more than 70% of treatment fractions where treatment adaptation is indicated.

Our principal objectives in this trial will be to determine the feasibility for online proton adaptive radiotherapy. If we can successfully deliver treatments for more than 70% of treatment fractions where treatment adaptation is indicated while maintaining the safety, then we will consider this study as having provided sufficient pilot data to support more widespread study of online proton adaptive radiotherapy. Historical controls reference 70% as the definition of feasibility, so we have utilized that for our primary endpoint. Basic descriptive statistics will be used to evaluate feasibility. The long-term goals will be to improve patient outcomes and care by improving target coverage and decreasing radiation toxicity.

Regarding toxicity, we will report descriptive statistics for acute toxicity at a three-month time point. Toxicity rates are anticipated to be identical or improved to those of other linear accelerator based SBRT treatments. Other than the online adaptation component of the treatment plan, patients will receive disease site specific standard-of-care dose and fractionation treatment plan. Therefore, further prospective toxicity assessments are not indicated. Given that no prior data exists for online adaptive proton radiotherapy, we will report descriptive statistics. Descriptive statistics will be calculated on all variables. Frequencies will be computed for all binary/categorical variables, and continuous variables will be summarized using medians, quartiles, and ranges. Patient satisfaction measured with PREMS will be evaluated using descriptive statistics. As a pilot study we will establish these baseline parameters.

For the dosimetry exploratory endpoints, non-parametric equivalents (Wilcoxon test) will be conducted to compare plan quality between simulated pre-plans and online adaptive plans. Further analysis may be conducted with ANCOVA to estimate how the baseline covariates associated simulated pre-plans and online adaptive plans. The ANCOVA will be presented with least square (LS) mean estimate. Two-sided 95% confidence intervals for the mean changes and p-values will also be reported.

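### The primary success rule does not say that the adapted plan must be the plan delivered, so on one available reading a fraction treated with the pre-plan counts as an adaptive success

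*Combined protocol and SAP*

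**What the plan says.** Section 11.1 sets the feasibility criterion as "successful completion of online adaptive proton radiotherapy workflow through treatment delivery in at least 70% of planned adaptive fractions". It then gives the rule for a single fraction: "Success will be defined as PARTy plan creation and delivery of the fraction using the study workflow in one on-table attempt". An unsuccessful fraction is one with "multiple attempts of the PARTy workflow for one treatment fraction without treatment delivery such that the study workflow is abandoned". The synopsis and the endpoint column of section 2.0 repeat these definitions.

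The treatment sections describe what happens at each session. Section 5.0: "Both plans will then be compared, and the plan deemed to be most appropriate will be carried out". Section 5.1.6, after the physician has reviewed both plans: "Subsequently, decision will be made if treatment will proceed with adapted plan or with initial pre-plan".

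Section 11.4 states the aim as "confirming that adaptive treatment can be delivered in more than 70% of treatment fractions where treatment adaptation is indicated". It evaluates feasibility with descriptive statistics and treats passing the 70% mark, with safety maintained, as enough to support wider study.

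**The concern.** The scoring sentence has two components: an adapted plan is created, and the fraction is delivered within the study workflow in one attempt. What is delivered is the fraction, not the adapted plan. An adapted plan is generated at every session under sections 5.0 and 5.1.6, so the first component would usually be met. If the study workflow means the daily procedure of those sections, the second can be met by giving the pre-plan.

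The rate could then partly measure whether the patient was treated that day, and not whether adaptive treatment could be delivered. This rate is the trial's only numerical decision criterion. The study-specific monitoring table in Appendix D would not reveal the difference: it lists the number of fractions completed and a yes/no for feasibility, but not which plan was given.

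**Working it through.** **Step 1. Apply the wording to each kind of fraction.** The broad reading takes the study workflow to be the daily procedure in 5.0 and 5.1.6. The narrow reading takes it to be the workflow in 1.4, which ends with the adapted plan approved and loaded.

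| Fraction | Broad reading | Narrow reading | Meets the failure definition? |
|---|---|---|---|
| A. Adapted plan created and delivered, one attempt | Success | Success | No |
| B. Adaptation indicated, adapted plan created in one attempt, pre-plan delivered | Success | Not a success | No: one attempt, and treatment was given |
| C. Several attempts, then pre-plan delivered | Not a success | Not a success | Not clearly: workflow abandoned, but treatment was given |
| D. Several attempts, nothing delivered, workflow abandoned | Not a success | Not a success | Yes |
| E. Adaptation not indicated, pre-plan delivered | Outside the denominator in 11.4; unclear in 11.1 | Same | No |

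Only row B can raise the numerator. Row C cannot, because it fails the one-attempt condition, but it has no clear label.

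**Step 2. Convert the threshold to counts.** The plan gives no power or sample-size calculation to reproduce. Section 11.3 sets 10 evaluable patients on clinical grounds and section 5.0 gives 5 fractions each, so there are at most 10 × 5 = 50 fractions. Since 0.70 × 50 = 35, at least 70% (11.1) needs 35 successes and more than 70% (11.4) needs 36.

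**Step 3. Score one assumed set of counts three ways.** Assume 30 fractions of type A, 10 of type B and 10 abandoned, with all 50 in the denominator at the start.

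- Type B as success: (30 + 10)/50 = 80%, feasible.
- Type B as failure: 30/50 = 60%, not feasible.
- Type B excluded: 30/(50 − 10) = 30/40 = 75%, feasible.

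With 25 of type A, 10 of type B and 15 others, the rates are 35/50 = 70%, 25/50 = 50% and 25/40 = 62.5%. Here the lenient score passes under at least 70% and fails under more than 70%.

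**Step 4. Chance of passing.** Treat the 50 fractions as independent, with success probability p, so that P(X ≥ k) = Σ C(50, x) pˣ (1 − p)⁵⁰⁻ˣ for x from k to 50. Assume 60% of fractions are delivered on the adapted plan. Strict scoring has p = 0.60. Lenient scoring has p = 0.60 + 0.10 = 0.70 or 0.60 + 0.20 = 0.80, if 10% or 20% of all fractions are type B.

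| Scoring | p | P(at least 35) | P(at least 36) |
|---|---|---|---|
| Strict | 0.60 | 0.096 | 0.054 |
| Lenient, 10% type B | 0.70 | 0.569 | 0.447 |
| Lenient, 20% type B | 0.80 | 0.969 | 0.939 |

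**The case against.** The strongest reply is that the text, read as a whole, already requires the adapted plan. The sentence before the scoring rule in 11.1 speaks of completing the online adaptive workflow through to delivery. Section 1.4, the prose that sets out a workflow, has no pre-plan branch: "The physician then conducts a final review of the adapted plan and grants approval", after which the formal plan is generated and loaded. An adapted plan rejected at review might on that account never count as created. Section 5.2 refers to a separate non-adaptive workflow, sections 5.0 and 5.1.6 do not use the word workflow, and 11.4 speaks of adaptive treatment.

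This stands as a reason not to say that pre-plan fractions do score as successes. It does not close the gap. Section 1.4 offers its workflow as a proposal, under preliminary studies, while 5.0 and 5.1.6 govern treatment on this trial and allow either plan.

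A reader might go further and infer that fallback to the pre-plan can never count against feasibility, or that the inflation is the same under any denominator. The documents support neither. Row C never enters the numerator. Excluding the type B fractions moves the example from 60% to 75%, so the effect depends on the denominator.

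It is also fair to say that this is a small descriptive pilot and that every rate in the illustration is assumed. That limits what can be said about the likely size of the effect. It does not remove the conflict.

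**Conclusion.** The point holds as a conflict between the scoring rule and the stated aim. Sections 11.1, 2.0 and the synopsis leave open whether a created but undelivered adapted plan is a success; section 11.4 requires adaptive delivery. The ambiguity is confined to row B for the numerator. Row C needs a label, and row E needs a denominator rule.

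Each type B fraction is worth 1/50 = 2 percentage points between lenient and strict scoring when all 50 fractions count. In the assumed example the rate is 80%, 60% or 75%, enough to reverse the conclusion. The documents give no rate for adapted delivery or for pre-plan use, so how often this would occur is unknown. The probabilities in step 4 also ignore correlation between fractions of the same patient and show direction only. The rule should be settled before any fraction is scored.

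**What to change.** In section 11.1, section 2.0 and the synopsis, replace the success sentence with: *Success is creation of the PARTy plan and delivery of that same adapted plan at that fraction in one on-table attempt.*

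With it:

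- Define the denominator as the fractions where adaptation was indicated, as in the objective in 2.0 and in 11.4, and use it throughout.
- State that any fraction in that denominator treated with the pre-plan, or not treated, is not a success. This also settles row C.
- Place fractions treated with the pre-plan because adaptation was not indicated outside the denominator, and report them separately with the reason. Without this, the stricter sentence would count appropriate non-adaptation as failure.
- Choose either at least 70% or more than 70% and use it everywhere.

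The cost is a wording change, one recorded item per fraction (plan delivered and reason), and possibly a lower reported rate. It changes how the endpoint is scored, not which plan a patient receives.

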11.2 Definition of Secondary and Exploratory Endpoints

Secondary

Toxicity: This will be evaluated throughout treatment and at 3 months post-end of SBRT using CTCAE v5.0. Grade 2+ radiation-related toxicity will be collected.

Patient satisfaction: This will be evaluated using patient reported experience measures (PREMs, Appendix E) at the end of treatment.

Dosimetry evaluation: PARTy dosimetric evaluation will be completed with a goal of comparing the dose to OARs and target coverage in online adapted treatment plan with the non-adapted treatment plan.

11.3 Sample Size Calculation

As a pilot study, the sample size is determined based on clinical considerations rather than statistical power. For our primary objective, our goal will be to report the description of online adaptive proton therapy treatment workflows, adaptation, and the time to delivery of first treatment fraction. Goal accrual will be 10 evaluable patients. For the exploratory objectives, sample size is also based on clinical considerations rather than statistical power.

11.4 Statistical Analysis Plan

The primary objective is to demonstrate that online proton adaptive radiotherapy is feasible by confirming that adaptive treatment can be delivered in more than 70% of treatment fractions where treatment adaptation is indicated.

Our principal objectives in this trial will be to determine the feasibility for online proton adaptive radiotherapy. If we can successfully deliver treatments for more than 70% of treatment fractions where treatment adaptation is indicated while maintaining the safety, then we will consider this study as having provided sufficient pilot data to support more widespread study of online proton adaptive radiotherapy. Historical controls reference 70% as the definition of feasibility, so we have utilized that for our primary endpoint. Basic descriptive statistics will be used to evaluate feasibility. The long-term goals will be to improve patient outcomes and care by improving target coverage and decreasing radiation toxicity.

Regarding toxicity, we will report descriptive statistics for acute toxicity at a three-month time point. Toxicity rates are anticipated to be identical or improved to those of other linear accelerator based SBRT treatments. Other than the online adaptation component of the treatment plan, patients will receive disease site specific standard-of-care dose and fractionation treatment plan. Therefore, further prospective toxicity assessments are not indicated. Given that no prior data exists for online adaptive proton radiotherapy, we will report descriptive statistics. Descriptive statistics will be calculated on all variables. Frequencies will be computed for all binary/categorical variables, and continuous variables will be summarized using medians, quartiles, and ranges. Patient satisfaction measured with PREMS will be evaluated using descriptive statistics. As a pilot study we will establish these baseline parameters.

For the dosimetry exploratory endpoints, non-parametric equivalents (Wilcoxon test) will be conducted to compare plan quality between simulated pre-plans and online adaptive plans. Further analysis may be conducted with ANCOVA to estimate how the baseline covariates associated simulated pre-plans and online adaptive plans. The ANCOVA will be presented with least square (LS) mean estimate. Two-sided 95% confidence intervals for the mean changes and p-values will also be reported.

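### The primary objective speaks of confirming a success rate above 70%, but the planned analysis is descriptive only, with no confidence interval and no allowance for several fractions per patient

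*Combined protocol and SAP*

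**What the plan says.** Section 11.4 sets the primary aim as to "demonstrate that online proton adaptive radiotherapy is feasible by confirming that adaptive treatment can be delivered in more than 70% of treatment fractions" where adaptation is indicated. If that is achieved with safety maintained, "then we will consider this study as having provided sufficient pilot data to support more widespread study of online proton adaptive radiotherapy". The threshold is explained by "Historical controls reference 70% as the definition of feasibility, so we have utilized that for our primary endpoint". The analysis is given in one sentence: "Basic descriptive statistics will be used to evaluate feasibility". The same section adds frequencies for binary variables. Its only 95% confidence intervals are in the paragraph on the exploratory dosimetry comparison.

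On size, Section 11.3 states "Goal accrual will be 10 evaluable patients", says this number does not rest on power, and describes the goal for the primary objective as reporting a description of the workflow. Section 5.0 states "The treatment will consist of stereotactic body radiation therapy, administered as 5 fractions".

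Section 11.1 words the threshold differently from Section 11.4: success "in at least 70% of planned adaptive fractions".

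**The concern.** The objective is worded as a conclusion about the true success rate, but the analysis yields only an observed percentage. Without an interval, a reader cannot tell a result that excludes rates below 70% from one that merely lands above it.

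The unit of analysis adds to this. The denominator counts fractions, and these come in groups of up to five from the same patient. Sections 5.1.8 and 1.7.1 describe patients who differ in site, anatomy, dose and constraints and who may spend 45 to 90 minutes on the table. Failures could therefore recur within a patient, in which case 50 fractions carry less information than 50 independent trials.

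At stake is how the result is read. Crossing 70% is the stated ground for wider study, and Section 1.6.1 says the pilot exists to supply data for a larger evaluation. The planner of that evaluation needs the precision of the rate as well as its value.

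**Working it through.** **Inputs from the documents.** 10 evaluable patients (Section 11.3); 5 fractions each (Section 5.0); threshold above 70% (Section 11.4) or at least 70% (Section 11.1). No alpha, power, alternative rate or ICC is stated.

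**The plan's own figure.** The 10 patients have no statistical derivation, so there is nothing to reproduce. The largest possible denominator is 10 × 5 = 50 fractions.

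**Smallest passing result.** 0.70 × 50 = 35, so more than 70% means at least 36/50 = 72%.

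**Interval with independent fractions.** The Clopper-Pearson limits are the 2.5% point of Beta(x, n − x + 1) and the 97.5% point of Beta(x + 1, n − x). For 36/50 these are Beta(36, 15) and Beta(37, 14), giving 57.5% to 83.8%.

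**Interval with within-patient correlation.** Design effect = 1 + (5 − 1) × ICC, and effective n = 50 / design effect. The same Beta limits are taken at 72% of the effective n. To allow for having only 10 patients, the effective n is also multiplied by (t with 49 df / t with 9 df)² = (2.010 / 2.262)² = 0.789. The ICC values are assumptions.

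| ICC | Design effect | Effective n | 95% CI for 72% | Effective n, 9 df | 95% CI, 9 df |
|---|---|---|---|---|---|
| 0.2 | 1.8 | 27.8 | 51.8% to 87.2% | 21.9 | 49.0% to 88.8% |
| 0.4 | 2.6 | 19.2 | 47.2% to 89.7% | 15.2 | 43.7% to 91.4% |

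**How often the rule passes.** This is the probability of at least 36 successes in 50: binomial for ICC 0, otherwise the sum of 10 independent beta-binomial counts of 5, each with parameters p(1 − ICC)/ICC and (1 − p)(1 − ICC)/ICC.

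| True rate | ICC 0 | ICC 0.2 |
|---|---|---|
| 50% | 0.1% | 1.3% |
| 60% | 5.4% | 11.8% |
| 65% | 18.8% | 26.0% |
| 70% | 44.7% | 46.9% |
| 80% | 93.9% | 87.7% |

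**Result whose lower limit exceeds 70%.** With independent fractions, 42/50 (84%) is the first, with an interval of 70.9% to 92.8%. With 9 patient-based degrees of freedom, even at design effect 1, 42/50 has a lower limit of 68.9%, so 43/50 is needed. Clustering raises the bar further.

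**Smaller denominators.** Section 5.1.6 allows the pre-plan to be delivered at any fraction, and Section 5.2 makes a patient evaluable after one fraction. If, for illustration, 25 fractions counted, 18/25 (72%) would pass with an interval of 50.6% to 87.9% under independence.

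**Threshold wording.** The two versions differ at exactly 35/50. Under at least 70%, the pass probabilities with independent fractions are 28.0% at a true 65% and 9.6% at a true 60%.

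**The case against.** The best defence is that this is a declared pilot. Section 11.3 disclaims power and describes a descriptive goal. Passing leads only to support for further study, and Section 11.4 also requires that safety be maintained. A point-estimate benchmark is an accepted progression rule in that setting. This stands, and it is why neither the benchmark nor the 10 patients is criticised here. It does not cover the wording of the objective or the absence of an interval, since estimation with stated precision is a pilot's main product.

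A second defence is that the plan omits an interval without forbidding one, and that Appendix D tabulates fractions completed and a yes/no feasibility entry for each patient. That is true, but the table is for monitoring and does not show successes over indicated fractions.

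A reader might infer something stronger: that failures will cluster, and that a pass is therefore compatible with a true rate near 50%. The documents do not support that as fact. They give no ICC, and some failures could come from equipment, quality assurance or staff learning, which need not follow the patient. With 50 independent fractions the lower limit is 57.5%; values near 50% need an assumed ICC of about 0.2 or more, or a reduced denominator. Nor is the rule lax against very poor performance: at a true 50% it passes 0.1% of the time, or 1.3% at ICC 0.2. The documents also define no rate as unacceptable.

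**Conclusion.** The point holds as a mismatch between claim and analysis. A result of 36/50 meets the Section 11.4 rule but leaves true rates down to 57.5% within its 95% interval, before any clustering is assumed. That conclusion needs only the 10 patients, the five fractions each and independence. The lower figures, about 52% to 47% at the effective sample size or 49% to 44% with 9 patient-based degrees of freedom, rest on an assumed ICC of 0.2 to 0.4 and should be read as a sensitivity range.

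It would go too far to conclude that the pilot is too small or its 70% benchmark invalid: the plan claims no power and attaches a modest decision to the result. The severity is a minor improvement.

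**What to change.** In Section 11.4:

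- Keep 70%, together with the safety condition, as a point-estimate benchmark for progression.
- Report the fraction-level success rate with a two-sided 95% confidence interval that accounts for clustering by patient, using a small-sample method named in advance. A Korn-Graubard interval, a cluster bootstrap, GEE with a small-sample correction or a beta-binomial model would each be reasonable.
- Name a fallback for the case in which every fraction succeeds, since the design effect cannot then be estimated. A patient-level exact interval is one option. For 10/10 patients its lower limit is 0.025^(1/10) = 69.2%, just under 70%, so the plan should say beforehand how a perfect result would be described.
- List successes over indicated fractions for each patient.
- Reword the objective so that a pass is reported as: *the observed rate met the 70% benchmark*. Use *confirmed* only if the lower limit exceeds 70%. That takes at least 42/50 by Clopper-Pearson with independent fractions, and more with clustering or patient-based degrees of freedom.
- Choose between at least 70% (Section 11.1) and more than 70% (Section 11.4), and use one wording throughout.

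The cost is a change of wording and a few lines of code, with no change to accrual or treatment. The downside is that the stated conclusion becomes less strong.

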5.1.8 Dose Constraints

As this is a feasibility study, patients participating in the trial will have various types of malignancies in different anatomical locations, clinical circumstances, and different prescribed doses and treatment schedules. The dose constraints for each patient will be specific to their individual anatomy and will be determined during the initial treatment planning process by the treating radiation oncologist. Specific dose constraints will be established on a case-by-case basis. Generally, dose constraints will adhere to standard of care institutional dose constraints employed here at WashU/BJC Radiation Oncology Department. Below is suggested dose constraints for 5 fraction SBRT. The dose constraints listed below may be modified based on individual patient's clinical scenario and discretion.

Structure	Goal	Variation
Brachial Plexus	D0.1cc < 30.5Gy	D 0.1cc < 32Gy
Chest Wall	D0.1cc < 43Gy	
Spinal Cord	D0.5cc < 25Gy	
Lungs	V20Gy < 10%	V20Gy < 15%
Esophagus	D0.5cc < 33Gy	D0.5cc < 36Gy
Heart	D0.1cc < 29Gy	D0.1cc < 38Gy
Liver - GTV	Critical Volume >700cc < 15Gy V10Gy < 70%	
Kidney	Bilateral mean <15 Gy	
Stomach	D0.5cc < 33Gy	D0.5cc < 36Gy
Duodenum	D0.5cc < 33Gy	D0.5cc < 36Gy
Small Bowel	D0.5cc < 33Gy	D0.5cc < 36Gy
Large Bowel	D0.5cc < 33Gy	D0.5cc < 36Gy
Rectum	D0.1cc < 38Gy	
Bladder	D0.1cc < 38Gy	

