5.2 Definitions of Evaluability

Endpoint	In order to be evaluable for this endpoint, a patient must...
Primary: feasibility of online proton adaptive radiotherapy	Have received at least one fraction of SBRT.
Secondary: G2+ toxicity at 3 months	
Exploratory: dosimetry evaluation and comparison to non-adaptive workflow	
Exploratory: PREMs	Have received at least one fraction of SBRT and completed PREMs.

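### The dosimetric comparison in Section 11.4 does not set the patient as the unit of analysis; if up to 50 plan pairs from 10 patients are analysed as independent, p-values are too small and confidence intervals too narrow

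*Combined protocol and SAP*

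**What the plan says.** Section 11.4 states that "non-parametric equivalents (Wilcoxon test) will be conducted to compare plan quality between simulated pre-plans and online adaptive plans". It adds that an ANCOVA with baseline covariates and least-squares means may follow, and that "Two-sided 95% confidence intervals for the mean changes and p-values will also be reported". It does not state the unit of analysis (fraction, patient or accumulated course), whether the Wilcoxon test is signed-rank or rank-sum, or how several fractions from one patient are handled.

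The structure of the data is set elsewhere:

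- Section 11.3: "Goal accrual will be 10 evaluable patients".
- Section 5.0: "The treatment will consist of stereotactic body radiation therapy, administered as 5 fractions". Of generating and comparing a pre-plan and an adapted plan, it says "This process will occur for each treatment".
- Section 5.1.6: at each session "the initial treatment pre-plan will be generated based on the anatomy of the day", alongside a new adapted plan.
- Section 5.2: the evaluability condition, read as covering dosimetry as well as feasibility, is "Have received at least one fraction of SBRT". Patients may therefore contribute different numbers of fractions.
- Section 5.1.8: "patients participating in the trial will have various types of malignancies in different anatomical locations", with dose constraints set patient by patient.

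**The concern.** The test is described as a comparison of plans, and each patient generates a new pair of plans at every fraction. Taken literally, a plan-level analysis has up to 50 pairs from only 10 independent patients. Fractions from one patient share tumour site, prescription, beam arrangement and neighbouring organs, so their differences are likely to resemble each other. A Wilcoxon test or ANCOVA that treats the pairs as independent overstates the information in the data.

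Feasibility, toxicity and patient experience are all to be summarised descriptively. The dosimetric comparison is therefore the only planned formal inference, and it supplies the trial's only planned p-values and confidence intervals. Section 1.6.1 says that the pilot is to provide data for a larger evaluation, and better coverage and organ sparing are the benefits hoped for. Error bars that are too narrow could make that signal look firmer than 10 patients can support.

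**Working it through.** **Is there a figure to reproduce?** No. Section 11.3 sets 10 patients on clinical grounds, without an alpha, power, effect size or standard deviation. The check is therefore how the stated test behaves on the data that the design produces.

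**Inputs from the documents.** Patients k = 10 (Section 11.3). Fractions per patient m = 5 (Section 5.0). Maximum pairs = 10 × 5 = 50.

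**Assumed inputs.** Within-patient ICC of the paired differences from 0 to 0.9, because no value is given. Two-sided alpha of 0.05, to match the 95% intervals. Normally distributed differences with no true mean effect.

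**Analytic step.** Design effect DE = 1 + (m − 1) × ICC. Effective number of pairs = 50 / DE. Approximate type I error when pairs are treated as independent = 2 × [1 − Φ(1.96 / √DE)]. At ICC 0.3, DE = 1 + 4 × 0.3 = 2.2, the effective number is 50 / 2.2 = 22.7, and the error is 2 × [1 − Φ(1.96 / 1.483)] = 18.6%.

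**Simulation.** 10,000 replicates of 10 patients × 5 fractions, using the signed-rank test and a t-based 95% interval on all 50 differences.

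| ICC | DE | Effective pairs | Analytic type I error | Simulated type I error, pooled | 95% CI coverage, pooled |
|---|---|---|---|---|---|
| 0 | 1.0 | 50.0 | 5.0% | 5.3% | 94.8% |
| 0.1 | 1.4 | 35.7 | 9.8% | 9.2% | 90.4% |
| 0.3 | 2.2 | 22.7 | 18.6% | 18.0% | 81.1% |
| 0.5 | 3.0 | 16.7 | 25.8% | 26.1% | 73.2% |
| 0.7 | 3.8 | 13.2 | 31.5% | 31.5% | 67.1% |
| 0.9 | 4.6 | 10.9 | 36.1% | 37.4% | 61.3% |

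Repeat runs of the same layout gave 9-10% at ICC 0.1, 17-18% at 0.3 and 24-26% at 0.5. Coverage in them was 89-90%, 81% and 73-75%.

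**Fewer fractions.** With 3 fractions per patient, pooled type I error is 7.2% at ICC 0.1 and 16.5% at ICC 0.5. The problem shrinks but remains.

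**The same data, one mean difference per patient (n = 10).** Signed-rank type I error is 4.3% to 5.4%, and coverage of the t-based interval is 94.5% to 95.5%, at every ICC from 0 to 0.9. The exact attainable two-sided size at n = 10 is 4.88%, and the smallest possible p-value is 2 / 2^10 = 0.002. A patient-level test is therefore valid and can still detect a consistent effect.

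**The case against.** The strongest reply is that Section 11.4 is silent, not wrong. It never says that the 50 pairs will be pooled as independent, and a signed-rank test on 10 patient summaries fits its wording and would be valid. The endpoint is exploratory in Sections 2.0, 5.2 and 11.4, although Section 11.2 prints it beneath a Secondary heading. No power is claimed for it, and the stated decision rests on feasibility above 70% with safety maintained. The ICC is assumed, and at zero there is no inflation.

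Most of this stands, and it limits the point to a conditional one. It does not remove the point: the text describes a comparison of plans, plans arise once per fraction, and the choice of unit is left open until after the data are seen.

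A reader might also infer four stronger things that the documents do not support:

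- **That the published results will be wrong.** This follows only if fractions are treated as independent, which is not stated.
- **That all five adapted plans are compared with one fixed pre-plan on one anatomy.** Section 5.1.6 puts the pre-plan on the anatomy of the day. The phrase in Section 11.4 about simulated pre-plans is at most ambiguous.
- **That an unpaired test is planned, with a large loss of power.** The pairing is unstated, but the reference to mean changes points towards within-unit differences. Any power figure would need an effect size and a correlation that the documents do not give.
- **That 14 structures mean 14 tests and a high chance of a false positive.** Section 5.1.8 offers its table as suggested and modifiable, and Section 11.4 does not say that each structure will be tested. A structure present in only 5 patients could not reach p < 0.05 in a valid patient-level test, because the minimum is 2 / 2^5 = 0.0625.

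**Conclusion.** The point holds in conditional form. Section 11.4 should fix the unit of analysis, the pairing and the handling of repeated fractions, because the literal plan-level analysis understates uncertainty. At full fractionation, a nominal 5% test would reject a true null 9-10% of the time at ICC 0.1, 18% at 0.3 and 24-26% at 0.5, and a nominal 95% interval would cover about 81% at ICC 0.3 and 73-75% at 0.5.

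These figures assume that fractions are pooled as independent, that all 10 patients complete 5 fractions, that differences are normal, and that the ICC lies in the range shown. The true ICC is unknown. Mixed sites and patient-specific constraints make zero implausible, but they do not identify a value.

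The consequence is confined to an exploratory endpoint. It affects how the dosimetric findings can be read and carried into later work, not the feasibility conclusion.

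**What to change.** Amend Section 11.4 as follows:

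- Name the patient as the unit of inference. At each fraction, define the difference as adapted plan minus pre-plan, both evaluated on the anatomy of the day.
- Average the differences within patient. Apply the Wilcoxon signed-rank test to the patient means and compute the 95% interval from the same means. This gives one value per patient even where the number of fractions varies.
- Alternatively, fit a mixed model to the fraction-level differences with a random patient effect and a small-sample correction, since there are only 10 clusters.
- If the optional ANCOVA is run, use the same patient-level data or include a random patient effect.

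The change is to SAP wording only and needs no extra patients, visits or data. The price is wider intervals and fewer small p-values. Limiting the tests to a few measures, or omitting the ANCOVA, would be a matter of preference and is not required by this point.
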